9.0 Statistical design with exploratory endpoints –

The primary efficacy endpoint is IgG response, defined as having improvement in IgG level by at least 25% at 6 months, compared to baseline. We are targeting an IgG response rate of 50% and we would not be interested in pursuing further if the IgG response rate is 20% or lower. Using Simon's optimal two-stage design, we will enroll 12 patients in the first stage and the trial will be stopped if there are 3 or less IgG responders among the first 12 patients. If there are 4 or more responders, we will continue the enrollment until 31 patients are reached. The effect of lenalidomide is demonstrated and worth pursuing further if among the total 31 patients, at least 10 patients achieve IgG response. This design is based on a type I error rate of 0.025 and a 90% power. Under the null hypothesis, the probability of early termination is 79% and the expected sample size is 16 patients. Patient enrollment will be suspended if there are not at least 3 IgG responders in the first 12 patients and not all 12 patients have been evaluated at 6 months. To account for a potential 10% early drop-out rate, we will enroll 35 patients so as to have 31 patients with both baseline and 6-month evaluations on IgG. Potential reasons for early dropouts are patients' choice, inability to return to our center or changes in CLL status that may require a different intervention. Sensitivity

analysis will be performed to assess the impact of early dropouts. For example, we will analyze the data counting early dropouts either as "failures" (the most conservative approach) or as "missing" (thus, excluded from the analysis) and evaluate the response rate in both scenarios. Also, since the treatment requires at least 3 months of therapy before seeing an effect on immunoglobulin levels, we will also perform a secondary analysis by including only those patients who have been treated for at least 3 months, while counting those early dropouts between 3 and 6 months as "failures".

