Lenalidomide-related toxicity (defined as any grade 3 or greater non-hematological toxicity) will be monitored using the method of Thall, Simon and Estey [16] and the study will be terminated early if toxicity occurs in more than 40% of patients. Specifically, denoting the probability of toxicity by p , the study will be stopped early if $\text{Prob}(p > 0.40 \text{ data}) > .95$. The above decision criterion will be applied in cohort size of 5. Assuming a beta (.4, .6) priori for p , the above decision criterion implies that we will stop the trial according to the table below. For example, the trial will be terminated if 4 or more patients experienced toxicities among the first 5 patients.

Number of patients	Number of patients with toxicities is at least
5	4
10	7
15	10
20	12
25	15
30	17

The operating characteristics of this study design based on 10,000 simulations are illustrated in Table 2.

Table 2. Operating Characteristics for Toxicity Monitoring Rule.

True toxicity rate	Prob (stop early)	Sample Size 25 th , 50 th and 75 th percentiles
0.20	0.006	35, 35, 35
0.30	0.039	35, 35, 35
0.40	0.152	35, 35, 35
0.50	0.447	10, 35, 35
0.60	0.808	5, 15, 30

For the primary analysis, we will estimate the rate of IgG response along with the 95% confidence interval. As secondary analyses, we will also estimate the rates of Pneumococcus and Influenza seroconversion response, as defined in the response criteria section, and the corresponding 95% confidence intervals. The study will be considered positive in regard to the secondary endpoints if seroconversion is observed in 60% or more of the subjects for at least one of the vaccinations given. Similar method will be used to estimate the rate of influenza or Pneumococcal pneumonia. The duration of IgG response will be estimated using the Kaplan-Meier method. The cytokine levels and serum properdin levels will be summarized using descriptive statistics and will be compared between IgG responders and non-responders using two-sample t-test or Wilcoxon rank-sum test, as appropriate.

Amendments, Deviations, Regulatory

Protocol Amendments

Any amendment to this protocol must be agreed to by the Principal Investigator and reviewed by Celgene. Amendments should only be submitted to IRB after consideration of Celgene review. Written verification of IRB approval will be obtained before any amendment is implemented.

Protocol Deviations

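### The primary 95% confidence interval has no stated method and no allowance for the futility stop, so an ordinary binomial interval could disagree with the two-stage test at 11 of 31

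*Protocol*

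**What the plan says.** Protocol Section 9.0, repeated in the SAP under the same heading, sets a single-arm two-stage test of the IgG response rate. The null rate comes from "we would not be interested in pursuing further if the IgG response rate is 20% or lower"; the target is 50%. The first-stage rule is "we will enroll 12 patients in the first stage and the trial will be stopped if there are 3 or less IgG responders". With 4 or more responders, "we will continue the enrollment until 31 patients are reached". Lenalidomide is judged worth pursuing "if among the total 31 patients, at least 10 patients achieve IgG response". The stated operating figures are type I error 0.025, power 90%, a 79% chance of early termination under the null, and an expected sample size of 16.

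Later in the same section the whole primary analysis is: "For the primary analysis, we will estimate the rate of IgG response along with the 95% confidence interval". Neither document names an estimator or an interval method, whether single-stage or two-stage. Neither says how the interval relates to the stopping rule or to the success cut-off.

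**The concern.** With no method named, an analyst would most likely divide responders by patients and attach a standard binomial interval. Such an interval treats the sample size as fixed. Here the sample size depends on the first 12 results, and the decision comes from a two-stage test.

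Two things are at stake. Close to the cut-off, the report could show an interval that includes the uninteresting rate of 20% beside a test that rejects 20% at 0.025. Whether that happens would depend on a method chosen after the data are seen. Some common intervals also fall short of 95% coverage under this design.

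**Working it through.** **Inputs (all from Section 9.0).** Null rate 0.20, target 0.50, first stage 12 patients with a stop at 3 or fewer, total 31 (so 19 in stage 2), success at 10 or more, type I error 0.025, power 0.90. The choice of interval method is an assumption, so a range of methods is shown. The calculations take exactly 12 and 19 evaluable patients.

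**1. Reproduce the plan's design figures.** X1 ~ Bin(12, p) and X2 ~ Bin(19, p).
- Early termination at p = 0.20: P(X1 ≤ 3) = 0.7946 (stated 79%).
- Expected size: 12 + 19 × (1 − 0.7946) = 15.9 (stated 16).
- Rejection probability for cut-off c: the sum over x = 4 to 12 of P(X1 = x) × P(X2 ≥ c − x).

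| Cut-off | Type I error (p = 0.20) | Power (p = 0.50) |
|---|---|---|
| 10 or more (as written) | 0.0506 | 0.921 |
| 11 or more | 0.02498 | 0.908 |

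For c = 11 at p = 0.20, the terms for x = 4, 5, 6, 7 and 8 are 0.00898, 0.00867, 0.00506, 0.00181 and 0.00040. With about 0.00006 for x ≥ 9, they sum to 0.02498. A search for the optimal design at these inputs returns 3/12 and 10/31, where success needs more than 10 responders. The stated 0.025 therefore goes with 11 or more. It also shows that 0.025 is one-sided, which matches the lower limit of a two-sided 95% interval.

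**2. Intervals near the cut-off.** The exact two-stage limits rank first-stage stops below all second-stage results. The lower limit solves P(result at least as high as observed) = 0.025, and the upper limit solves P(result at most as high) = 0.025. As a hand check, Wald at 11/31 is 0.3548 ± 1.96 × √(0.3548 × 0.6452/31) = 0.3548 ± 0.1684.

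| Method | 10/31 | 11/31 | Includes 20% at 11/31? |
|---|---|---|---|
| Clopper-Pearson | 16.7-51.4% | 19.2-54.6% | yes |
| Wald | 15.8-48.7% | 18.6-52.3% | yes |
| Wilson | 18.6-49.9% | 21.1-53.0% | no |
| Exact two-stage | 17.8-57.7% | 20.0-58.6% | no (lower limit 20.003%) |

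Agresti-Coull (21.0%) and Jeffreys (20.5%) also exclude 20% at 11/31. At 12/31 and above every method excludes 20%. At 10/31 every method includes it, the two-stage interval among them.

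**3. Coverage under the two-stage design.** This is the total probability of all outcomes whose interval contains the true rate.

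| True rate | Wald | Wilson | Clopper-Pearson | Two-stage |
|---|---|---|---|---|
| 20% | 92.1% | 97.5% | 98.9% | 97.5% |
| 30% | 88.9% | 96.3% | 96.3% | 96.3% |
| 40% | 87.8% | 94.2% | 96.6% | 96.7% |
| 50% | 87.3% | 92.6% | 96.0% | 96.6% |

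Adding true rates of 25%, 35% and 45%, Wald runs from 83.0% (at 25%) to 93.4% (at 35%). Wilson stays within 92.6-97.5% and Clopper-Pearson within 96.0-98.9%. The same sum in steps of half a point shows Clopper-Pearson dipping to 94.2% near 48.5%, while the two-stage interval stays above 95%.

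**4. Bias of the plain rate, in percentage points.**

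| True rate | Over both stages | Given stage 2 is reached |
|---|---|---|
| 20% | −2.2 | +6.7 |
| 30% | −3.3 | +4.1 |
| 40% | −2.6 | +2.1 |
| 50% | −1.2 | +0.8 |

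After stage 2 with s responders, the UMVUE is Σ C(11, x−1) C(19, s−x) ÷ Σ C(12, x) C(19, s−x), with x from 4 to min(12, s). It gives 39.2% at 10/31 (plain 32.3%) and 40.8% at 11/31 (plain 35.5%).

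**The case against.** The strongest reply is that little depends on this. The go/no-go rule uses the count, so no decision changes. Once the cut-off matches the stated 0.025, a conflict due purely to a single-stage method can arise at one result only, 11/31, and only with some methods. That result has probability 1.4% at a true rate of 20%, about 9% at 30% and at 40%, and 2.8% at 50%. The two-stage limit clears 20% there by only 0.003 points. All of this stands and limits the severity.

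A reader might also infer four stronger things that the documents or figures do not support.

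- That the plan prescribes a single-stage interval. It prescribes none; single-stage is only the likely default.
- That the plain rate understates the response rate. It does so by 1 to 3 points on average over both stages. Among trials that reach stage 2, the only ones that can succeed, the bias is upward.
- That coverage fails in general. The marked shortfall is Wald's, and much of that is a small-sample defect: with no interim look, its coverage at a true rate of 25% is already 90.6% for n = 31 and 82.7% for n = 12.
- That a two-stage interval would always agree with the written success rule. At 10/31 it does not.

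Nor is the UMVUE a clear replacement for the plain proportion. Its mean squared error is higher at a true rate of 20% (0.0127 against 0.0081) and at 30% (0.0147 against 0.0117), and lower only at 40-50%. Given stage 2, its upward bias exceeds the plain rate's (+17.2 points against +6.7 at a true rate of 20%).

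**Conclusion.** The point holds as a gap in specification, and it is minor. The primary interval has no named method, although the design has a futility stop. At 11/31 the choice of method decides whether the interval includes 20%, while the two-stage test rejects 20% at p = 0.02498. Wald would cover 83-93% and Wilson about 93-97.5% over the true rates checked; Clopper-Pearson shows no material under-coverage.

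The exact two-stage interval is preferred because it inverts the design's own 0.025 test. With a cut-off of 11 it therefore agrees with the decision at every count. With the written cut-off of 10 a conflict remains at 10/31, and its source is the mismatch between that cut-off (0.0506) and the stated 0.025, not the interval method.

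The figures assume 12 and 19 evaluable patients, a one-sided 0.025 and stage-wise ordering.

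**What to change.** In the primary-analysis sentence of Section 9.0, in both Protocol and SAP, put:

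*The primary 95% confidence interval for the IgG response rate will be the exact interval from the two-stage sampling distribution with stage-wise ordering, computed with the stage sizes actually evaluated. The observed proportion will be reported, with the UMVUE beside it as a bias-adjusted estimate.*

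The reference to actual stage sizes is needed because the plan enrols 35 to obtain 31 evaluable patients and analyses dropouts both as failures and as missing, so the denominator may not be 31. Say which of those sets the primary interval uses. Report the two-stage p-value as well, because a lower limit of 20.003% prints as 20.0%.

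Separately, correct the cut-off and type I error where the two-stage rule is stated in Section 9.0: the stated 0.025 needs at least 11 of 31. The interval change cannot do this.

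The cost is one sentence and a few lines of code, with no extra patients or data. The downside is an interval about 0.4 to 2.6 points wider on average than Clopper-Pearson at true rates of 20-50%.

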Lenalidomide is an immunomodulatory agent related to thalidomide. This oral agent induces clinical responses in patients with CLL. Its mode of action is pleiotropic, affecting the bone marrow and tumor microenvironments, angiogenesis, T cell immune synapse dysfunction, antibody production, regulatory T cells numbers and function and other unknown mechanisms. When patients with CLL received lenalidomide as initial treatment of their disease, improvement in serum levels of immunoglobulins (IgG, IgA and IgM) was observed in a subset of patients [9]. We demonstrated that out of 16 patients who had low IgG level (<700 mg/dL) before therapy, 8 patients (50%) showed a normalization of IgG after 15 cycles and another 3 (19%) showed a rise in IgG of >50% from that of baseline. [9]. In a parallel study from the same patient cohort, we showed that treatment with lenalidomide was also followed by normalization of T cell number

and function [10]. Lapalombella and colleagues have also shown that lenalidomide can enhance CD154 expression on CLL cells and enhance antibody producing ability of B cells in vitro and ex vivo further supporting our hypothesis that lenalidomide could have a positive immunomodulatory effect in patients with CLL [11].

Therefore, we propose to conduct a single arm prospective clinical trial to assess the efficacy of lenalidomide in improving immunoglobulin levels and to potentiate antibody responses to immunizations with influenza and pneumococcal vaccination in patients with CLL.

A low dose of lenalidomide, 5 mg, will be administered three times a week with the plan to escalate to daily dosing in the case of no response. The rationale for the low dose is the potential to obtain an immunoresponse while avoiding the risk for myelosuppression. In our previous experience increase in immunoglobulin levels were seen in patients receiving lenalidomide, 5 mg every-other-day.

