3.0 Treatment Plan

We will administer lenalidomide at the dose of 5 mg/day on Monday, Wednesday and Friday for 3 months. If IgG levels improve by at least 25% of baseline, we will continue lenalidomide administration 3 months on and 3 months off for 2 years. If IgG levels do not improve we will increase the frequency of lenalidomide to 5 mg/day for additional 3 months and if response is achieved, lenalidomide will be continued at 5mg/day 3 month on/3 month off for a total of 2 years. Seasonal influenza vaccination (*Trivalent Influenza Vaccine, Fluarix, quadrivalent*) will be administered yearly, during the fall/winter season and pneumococcal immunization (Pneumococcal Polysaccharide Vaccine, Pneumovax)

will be administered once between month 6 and month 21. Patients, who have received the Pneumovax vaccine within last 5 years, will not receive Pneumovax vaccination.

Serum levels of all the immunoglobulin subclasses will be measured at baseline and every 3 months (+/- 3 weeks) during therapy. Serum levels of antipneumococcal capsular polysaccharide antibodies will be measured before, 4 weeks (+/- 2 week) and 3 months (+/- 3 weeks) after pneumococcal vaccination and at end of the study (to assess sustainable antibody responses) by ELISA. Haemagglutination inhibition antibody titres (HAI) will be assessed by WHO influenza reagent kit, before vaccination, 4 weeks (+/- 2 week) and 3 months (+/- 3 weeks) after influenza vaccination [12]. Influenza specific quantitative and qualitative CD8+ and CD4+ T cell responses will be determined by multiparameter flow cytometry technique from stored PBMC's from the patients before vaccination, 4 weeks (+/- 2 week) and 3 months (+/- 3 weeks) after influenza vaccination and at the end of the study [13, 14].

Dosage form

Lenalidomide will be supplied by Celgene Corporation as 2.5mg and 5mg capsules for oral administration.

Prescribing Information

Lenalidomide (Revlimid®) will be provided to research subjects for the duration of their participation in this trial at no charge to them or their insurance providers. Lenalidomide will be provided in accordance with the Celgene Corporation's Revlimid REMS® program. Per standard Revlimid REMS® program requirements, all physicians who prescribe lenalidomide for research subjects enrolled into this trial, and all research subjects enrolled into this trial, must be registered in, and must comply with, all requirements of the Revlimid REMS® program.

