6.0 Evaluation during the Study

Complete blood counts (white blood cell, hemoglobin, platelets and differential), serum chemistry, basic metabolic profile, (sodium, potassium, chloride, CO₂, BUN, creatinine and glucose) will be monitored once every two-four weeks (+/- 4 days) while on lenalidomide.

At 3 months (+/- 3 weeks), patients will have a physical examination, CBC with differential and chemical survey, serum beta-2-microglobulin and IgA, IgG, IgM levels, flow cytometry (CD4+, CD8+). Pregnancy tests for females of childbearing potential and Risks of Fetal Exposure, Pregnancy Testing Guidelines and Acceptable Birth Control Methods, will be discussed with the patients.

Pneumococcal vaccination: Serum levels of antipneumococcal capsular polysaccharide antibodies will be measured before, 4 weeks (+/- 2 week) and 3 months (+/- 3 weeks) after vaccination and at the end of the study (to assess sustainable antibody responses) by ELISA. Influenza vaccination: Haemagglutination inhibition antibody titres (HAI) will be assessed by WHO influenza reagent kit before, 4 weeks (+/- 2 week) and 3 months

(+/- 3 weeks) after vaccination and at end of the study (to assess sustainable antibody responses) [12]. Influenza specific quantitative and qualitative CD8+ and CD4+ T cell responses will be determined by multiparameter flow cytometry techniques from stored PBMC's from the patients before vaccination, 4 weeks (+/- 2 week) and 3 months (+/- 3 weeks) after vaccination [13, 14]. Serum samples for cytokine levels (properdin, IFN- γ , IL-10, TNF- α , BAFF, IL-8, CCL3, and CCL4) will be stored before influenza vaccination at 4 weeks (+/- 2 week), 3 months (+/- 3 weeks) and at the end of the study). PBMC's will be stored at baseline, 4 weeks (+/- 2 week) and 3 months (+/- 3 weeks) after influenza vaccination to determine by multiparameter flow cytometry technique changes in influenza specific quantitative (using HLA-A2 restricted FluMP pentamer) and qualitative (using CD107a, IFN-gamma, IL-2 and TNF-alpha by intracellular staining) CD8+ and CD4+ T cell responses, as described [15].

Criteria for study discontinuation:

Treatment with study drug is discontinued and the patient will be removed from study when any of the following occurs:

1. Lack of response
2. Adverse event(s) that in the judgment of the investigator or the patient may cause severe or permanent harm or which rule out continuation of the study drug
3. Withdrawal of consent
4. Lost to follow-up

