8.0 Criteria for Response

Response criteria -

Ig response – Only IgG levels will be considered for response. IgG levels will be measured as mg/dL by nephelometry (normal range 700-1,600 mg/dL). Response will consist of normalization or improvement by 25% of baseline levels at 6 months during therapy.

Response criteria for the immunization –

Quadrivalent Influenza Vaccine (Fluvarix). HI assay was performed as previously described. Samples were assayed at baseline, 4 weeks (+/- 2 week) and 3 months (+/- 3 weeks) post-vaccination. Response or protection to influenza vaccination was defined as > 40 HU or a fourfold increase in HI titer at 4 weeks (+/- 2 week) and 3 months (+/- 3 weeks) post vaccination, against any of the three strains.

Assessment of the functionality of antigen-specific CD8+ and CD4+ T cells will be performed by intracellular cytokine staining for interferon (INF)-g and tumor necrosis factor (TNF)-a and evaluation of CD154 expression and CD107a cytotoxicity. In brief, PBMCs will be thawed and stimulated for 24 hours with or without the seasonal

influenza vaccine [A/Brisbane/59/2007(H1N1)-, A/Brisbane/10/2007 (H3N2)- and B/Florida/30/2008-like strain; CSL Biotherapies, Hattersheim, Germany]. A response will be considered positive if the % of antigen-specific IFN- γ -, TNF- α -, or CD107a-expressing T cells is ≥ 2 -fold higher than background (unstimulated PBMCs) and if there is a minimum of 0.05% antigen-specific T cells (after subtracting the background or FMO fluorescence minus one).

Pneumococcal Polysaccharide Vaccine - Seroconversion will be defined as at least a two fold increase in levels of antipneumococcal capsular polysaccharide (PCP) IgG antibody or achievement of concentration of $>0.5\mu\text{g/ml}$ in anti-pneumococcal capsular polysaccharide antibody titer (against 6 serotypes). They will be measured before, 4 weeks (+/- 2 week) and 3 months (+/- 3 weeks) post vaccination using ELISA and at the end of the study.

Exploratory Endpoints:

1. Infection rates of influenza or Pneumococcal pneumonia will be recorded during the study.
2. Sustained immunoglobulin responses will be recorded along with serological responses to both the vaccines.
3. Sera will be analysed for cytokine levels and properdin levels.

Correlative studies –

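### Patients removed for lack of IgG response leave as the Pneumovax window opens, so the pneumococcal part of the 60% rule is measured almost only in IgG responders, and its denominator is not defined

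*Protocol*

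**What the plan says.** - **Response.** Protocol Section 8: "Only IgG levels will be considered for response", and "Response will consist of normalization or improvement by 25% of baseline levels at 6 months during therapy".
- **Dosing.** Section 3 continues a patient whose IgG has risen by at least 25% at month 3, on a 3-months-on, 3-months-off schedule for 2 years. For the others: "If IgG levels do not improve we will increase the frequency of lenalidomide to 5 mg/day for additional 3 months", with treatment going on only if they then respond.
- **Removal.** Section 6: "Treatment with study drug is discontinued and the patient will be removed from study when any of the following occurs". The first item listed is "Lack of response". No time is attached to it, and no titre sampling after removal is described.
- **Pneumococcal vaccine.** Section 3: Pneumovax "will be administered once between month 6 and month 21", and not at all if the patient had it within the last 5 years. Titres are taken before the dose, at 4 weeks (+/- 2 weeks) and 3 months (+/- 3 weeks) after it, and at the end of the study.
- **Influenza vaccine.** Yearly in fall/winter, so a dose can fall before month 6.
- **Success rule.** Section 9 and the SAP: the secondary endpoints are positive if "seroconversion is observed in 60% or more of the subjects for at least one of the vaccinations given". Neither document says who the subjects are or how a patient without a titre is counted.
- **Aim.** Section 2 states the purpose as to "potentiate antibody responses to immunizations with influenza and pneumococcal vaccination in patients with CLL".

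**The concern.** Whether a patient contributes a pneumococcal result depends on an outcome observed after treatment began, the IgG rise, and that outcome is itself a measure of antibody production. If the patients who raise their IgG are also the ones more able to seroconvert, the measured rate exceeds the rate in the treated population, with or without any effect of lenalidomide on vaccination.

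The trial has no control arm to expose this. The only pneumococcal background figure, in Section 2 (no effective response in 75%), is for patients with CLL, not for IgG responders. Because the rule needs only one vaccine, this rate alone can make the study positive on its secondary endpoints. The influenza rate under the same rule can describe a different, less selected group.

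**Working it through.** **Step 1: timeline.** The documents give no figure to reproduce for the 60% rule (no sample size, error rate or power), so the first check is one of sequence.

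- Month 3: IgG is checked. Improvers continue; the others move to daily dosing.
- Month 6: response is judged (Section 8), and the extra 3 months end (Section 3). Removal at about month 6 is inferred from these two; Section 6 gives no time.
- Month 6: earliest Pneumovax dose.
- Month 6 + (4 - 2) weeks = month 6 + 2 weeks: earliest post-vaccination titre.

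A patient removed at month 6 can have a pre-vaccination sample, and even a dose that day, but no post-vaccination titre after leaving. Those who can be measured are IgG responders, plus any month-3 improver who falls below +25% at month 6 but is kept on by Section 3.

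**Step 2: how many can be measured.** Inputs from Section 9: 31 evaluable patients, a 50% target and a printed success cut-off of 10 responders.

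- At the target: 0.50 x 31 = 15.5, about 16 responders; 15 of 31 (48%) are not measured.
- At the cut-off: 10 responders; 21 of 31 (68%) are not measured.

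The few month-3 improvers kept on would raise these numbers of measured patients; the 5-year Pneumovax exclusion would lower them.

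**Step 3: two readings of the denominator.** The rule passes at the smallest whole number that is at least 0.6n: 6 of 10, 10 of 16, 19 of 31.

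| | 16 responders | 10 responders |
|---|---|---|
| Measured patients only: smallest pass | 10/16 = 62.5% | 6/10 = 60% |
| Exact (Clopper-Pearson) 95% CI | 35-85% | 26-88% |
| Same count over all 31 | 10/31 = 32% | 6/31 = 19% |
| All 31, missing = failure: highest possible rate | 16/31 = 52% | 10/31 = 32% |

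Under the first reading a pass can rest on a selected group. Under the second the rule cannot be met on pneumococcus at either split, because 19 seroconverters are needed and at most 16 or 10 patients are measured. With a true IgG response rate of 50%, the chance of 19 or more responders among 31 is 0.14.

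**Step 4: possible size of the inflation.** The documents give no seroconversion rate by IgG response. Let s1 be the rate in responders and s0 the rate in non-responders, with the rate over all 31 = (16 x s1 + 15 x s0)/31 held near 25%. That 25% is borrowed from Section 2 (100% - 75%) as an assumption. Chance of passing = P(Bin(16, s1) >= 10) if responders only, or P(Bin(16, s1) + Bin(15, s0) >= 19) if all 31 were measured.

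| s1 / s0 (assumed) | Rate over all 31 | Pass, responders only | Pass, all 31 measured |
|---|---|---|---|
| 25% / 25% | 25% | 0.2% | <0.1% |
| 30% / 20% | 25% | 0.7% | <0.1% |
| 35% / 15% | 25% | 2.3% | <0.1% |
| 40% / 10% | 25% | 5.8% | <0.1% |
| 50% / 0% (extreme) | 26% | 23% | 0 |

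As a check, equal rates of 60% in both groups give 53% against 52%. Without concentration in responders the selection does little harm.

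**The case against.** **Not only IgG responders.** A reader might infer that the pneumococcal subjects can only be IgG responders and that nobody else has any titre. The documents do not support this. A month-3 improver is in the off period during months 3 to 6, may be below +25% at month 6, and is still continued by Section 3. A pre-vaccination sample is possible for anyone. Since IgG is measured to +/- 3 weeks, a 2-week post-vaccination titre could on paper precede a late IgG result. These are narrow exceptions; patients who never improve still go unmeasured.

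**Direction of bias.** A reader might also infer that the rate must be inflated. Who is measured follows from the text; who is counted does not. If missing titres count as failures, the error runs the other way. The words about vaccinations given lean towards vaccinated patients but do not settle it.

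**Size.** The 25% figure comes from a study of vaccination with GM-CSF. Its definition of an effective response is not shown to match Section 8 (a twofold rise or more than 0.5 µg/ml). With mild concentration the chance of a spurious pass is small. This stands, so only a range can be given.

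**Intent and importance.** Judging vaccine response in patients who continue lenalidomide is a defensible design, and this is a secondary endpoint reported with a confidence interval. That stands too, but no passage says it is intended, and a confidence interval shows the small number, not the selection.

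**Conclusion.** The concern holds in this form: the written rules leave patients removed for lack of IgG response without a post-vaccination pneumococcal titre, so the pneumococcal rate is measured almost only in patients whose IgG rose, while the denominator of the 60% rule is undefined. This is more than a missing detail, because the rate alone can make the study positive on the secondary endpoints.

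The conclusion that the group is selected rests on one inference, removal at about month 6, and on no assumed rates. The size of any inflation does rest on assumed rates: at about 25% overall, the chance of passing runs from 0.2% to 5.8% for the moderate cases and reaches 23% only if no non-responder seroconverts. The documents do not show where in this range the truth lies, nor that inflation occurs at all. The primary IgG decision at month 6 is not affected.

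**What to change.** In Section 9 and the SAP:

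1. State the pneumococcal denominator of the 60% rule.
2. Report the rate, with its 95% CI, as the rate among patients continuing lenalidomide after IgG response.
3. Do not let that rate alone make the study positive on the secondary endpoints.
4. Beside it, report the rate over all vaccine-eligible patients reaching month 6, with missing titres as failures. Section 9 already uses this approach for IgG dropouts.

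This takes a few sentences and no extra patients, visits or samples. The downside is that the secondary positivity claim then rests on influenza alone.

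Optional, as a design choice for the sponsor: offer Pneumovax and the 4-week and 3-month titres to patients stopping for IgG non-response, and report them separately because they are off drug. At the 50% target this is at most about 15 doses, 15 x 3 = 45 ELISA samples (before, 4 weeks, 3 months) and two extra visits per patient. Responders should keep the month 6-21 window; forcing their dose to month 6 would place month-3 responders at the end of an off period.

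### The influenza and pneumococcal pneumonia rate is planned as a simple proportion over unequal follow-up, so it has no defined time base and shifts with the IgG response rate.

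*Protocol*

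**What the plan says.** Protocol Section 8.0 lists infection first among the exploratory endpoints: "Infection rates of influenza or Pneumococcal pneumonia will be recorded during the study". It gives no time point, season or denominator.

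Section 9.0, and the SAP in the same words, gives the analysis: "Similar method will be used to estimate the rate of influenza or Pneumococcal pneumonia". Earlier in the same paragraph the plan states that "we will also estimate the rates of Pneumococcus and Influenza seroconversion response", with 95% confidence intervals. That is the method the sentence points back to. Kaplan-Meier estimation is named next, but only for duration of IgG response. The dropout sensitivity analyses in Section 9.0 concern IgG response, not infection.

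Time on study is set elsewhere:

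- Section 3.0, for patients whose IgG improves: "we will continue lenalidomide administration 3 months on and 3 months off for 2 years".
- Section 3.0, for those whose IgG does not improve: "we will increase the frequency of lenalidomide to 5 mg/day for additional 3 months", with treatment going on to 2 years if they then respond.
- Section 6.0, criteria for study discontinuation: "Treatment with study drug is discontinued and the patient will be removed from study when any of the following occurs". Lack of response heads the list.
- Section 3.0, on influenza vaccine: it "will be administered yearly, during the fall/winter season".
- Section 9.0 allows for 10% early dropout.

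**The concern.** A proportion of patients infected can be interpreted when everyone is observed for the same period. Here the period depends on the primary outcome: an IgG responder can be observed for 2 years, while a non-responder leaves at about 6 months. An early leaver counts as one full patient without infection, although most of the 2 years was never observed. Calendar time adds to this. A 6-month stay may include no influenza season or one, depending on entry date, whereas a 2-year stay spans two.

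The resulting figure is called a rate but has no time unit. It cannot be set beside an outside infection rate, and it would differ between two trials with the same infection hazard but different IgG response rates. Section 2.0 gives infection as a main reason for the trial, and this is the only planned endpoint that measures it, so the figure is likely to be quoted.

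**Working it through.** The documents state no infection rate, so there is no figure to reproduce. The check asks how far the planned proportion moves when only the IgG response rate changes.

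**Inputs from the documents.** 35 patients enrolled and 10% early dropout (Section 9.0). Follow-up of 2 years for responders and about 0.5 years for non-responders (Sections 3.0 and 6.0 together). Response rates of 50% and 20%, the design's target and its upper bound for an uninteresting result: "We are targeting an IgG response rate of 50% and we would not be interested in pursuing further if the IgG response rate is 20%".

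**Assumptions.** A constant infection hazard L of 0.10 per year, with a range of 0.05 to 0.30. Dropouts leave at 0.25 years. A third response rate of 70%, for illustration.

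**Formulas**, for response rate r:

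- Expected proportion = 0.1 × (1 − exp(−0.25L)) + 0.9(1 − r) × (1 − exp(−0.5L)) + 0.9r × (1 − exp(−2L))
- Mean follow-up in years = 0.1 × 0.25 + 0.9(1 − r) × 0.5 + 0.9r × 2

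**At L = 0.10** the three risks are 0.0247, 0.0488 and 0.1813.

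- r = 0.20: 0.0025 + 0.72 × 0.0488 + 0.18 × 0.1813 = 0.070
- r = 0.50: 0.0025 + 0.45 × 0.0488 + 0.45 × 0.1813 = 0.106
- r = 0.70: 0.0025 + 0.27 × 0.0488 + 0.63 × 0.1813 = 0.130

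| IgG response | Mean follow-up (years) | Patient-years, n = 35 | Planned proportion | Expected infections (0.10 × patient-years) | Infections per patient-year |
|---|---|---|---|---|---|
| 20% | 0.75 | 26.1 | 7.0% | 2.6 | 0.10 |
| 50% | 1.15 | 40.2 | 10.6% | 4.0 | 0.10 |
| 70% | 1.42 | 49.7 | 13.0% | 5.0 | 0.10 |

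The hazard is the same in every row. The proportion nearly doubles from first to last (13.0 / 7.0 = 1.9), while the person-time rate does not move.

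**Against fixed periods.** The 1-year risk is 1 − exp(−0.10) = 9.5% and the 2-year risk is 1 − exp(−0.20) = 18.1%. All three proportions are below the 2-year risk. At 50% and 70% response they are above the 1-year risk; at 20% response the proportion is below it.

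**Other hazards.** At 50% response and hazards of 0.05, 0.10, 0.20 and 0.30, the proportion is 5.5%, 10.6%, 19.6% and 27.3%, or 58% to 60% of the corresponding 2-year risk (9.5%, 18.1%, 33.0%, 45.1%). At 20% response it is 38% to 42% of that risk, and at 70% response 71% to 73%.

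**Precision.** With about 4 events, the exact 95% interval for 4 of 35 is 3.2% to 26.7%. Exact Poisson limits for 4 events are 1.09 and 10.24; divided by 40.25 patient-years (35 × 1.15) they give 0.027 to 0.254 per year.

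**The case against.** The strongest reply is that little hangs on this figure. The endpoint is exploratory, none of the three objectives in Section 1.0 mentions infection, and the stopping and success rules use IgG response, toxicity and seroconversion only. With about four events any interval is wide, and the interval for 4 of 35 already covers both the 1-year and the 2-year risk. All of this stands, and it limits the severity.

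Three stronger readings are tempting, and the documents do not support them.

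- A reader might infer that the infection rate will be understated. That needs a target period, and the plan sets none. The proportion is below the 2-year risk but can exceed the 1-year risk.
- A reader might infer that a failing treatment will look protective. The trial has a single arm and names no historical infection rate or threshold against which the figure could look favourable.
- A reader might infer a confounded comparison of infections between IgG responders and non-responders. Section 9.0 plans that comparison for cytokine and properdin levels only.

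A further reply is that Kaplan-Meier estimation is no clean remedy. Non-responders leave at about 6 months, so later estimates rest largely on responders. If persistently low IgG raises infection risk, the censoring is informative. That stands, and it is why the person-time rate should lead. The person-time rate does not remove this selection either, but it states the time actually observed.

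The constant hazard is also a simplification, since influenza is seasonal. This affects the size of the illustration, not the lack of a time base, and it is a reason to report influenza by season as well.

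**Conclusion.** The point holds as a minor one. The plan names a method, a proportion with a 95% confidence interval, that does not suit an endpoint observed for about 6 months in some patients and 2 years in others. At an assumed hazard of 0.10 per year the figure runs from 7.0% to 13.0% as the response rate goes from 20% to 70%, with no change in infection risk. It has no fixed direction of error, because no reference period is set.

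This rests on four things: that the infection sentence refers back to the seroconversion method, its only natural antecedent; that infection recording ends on removal from study, since no later infection follow-up is described; that non-responders leave at about 6 months, which follows from Sections 3.0 and 6.0 read together; and, for the sizes only, on the assumed hazards and dropout time.

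**What to change.** In Section 9.0 and the SAP, replace the infection sentence with wording such as: Influenza and pneumococcal pneumonia will each be reported as the number of infections divided by patient-years at risk, counted from first dose to last study contact, with an exact Poisson 95% confidence interval. Influenza will also be reported per influenza season at risk.

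Any Kaplan-Meier cumulative incidence of first infection, for example at 12 months, should be supplementary and carry a note that removal for lack of IgG response may make censoring informative.

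The change affects neither sample size nor treatment. It does need the date of each infection, the dates that bound each influenza season, and a case definition. The documents do not confirm that these are captured: Section 8.0 speaks only of recording rates, and Section 7.0 has infections that accompany myelosuppression summarised in reports instead of filed as individual adverse drug reactions. The sponsor should check the case report form. The intervals will remain wide because few events are expected.
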